6.2.2 Enrollment, Baseline, and/or Randomization

Enrollment

Once caregiver eligibility has been established, a caregiver will be defined as enrolled in this study.

Baseline Assessments

All baseline assessments will be completed by caregivers. These self-administered assessment tools will be sent electronically to caregivers via secure email from each of the two participating clinical sites once they are enrolled in the study. Instructions will be provided to caregivers about

how to complete and return baseline assessments, either via return secure email or by uploading them to the secure EHR portal. Baseline assessment tools will include:

- Demographics: age, sex, race, ethnicity, relationship to older adult with ADRD (e.g., spouse, significant other, daughter), co-residence with older adult with ADRD, employment status, and number of hours per week providing care to person with ADRD
- Caregiver mastery: measured using a 4-item self-perceived caregiving competence scale⁵³
- Caregiver reactions to memory and behavior problems: 24-item scale capturing caregiver reactions to 24 memory and behavior problems⁵⁴
- Perceived Stress Scale: 14-item measure of the degree to which situations in one's life are appraised as stressful⁵⁵

Randomization

The administrative study coordinator will electronically access the appropriate study site's randomization string (strings will be generated by the study biostatistician, see Section 4.3) after a caregiver returns completed baseline assessment forms. Randomization results will reveal whether the caregiver is assigned to the Tele-Savvy program or to the attention control group. Randomization will be performed within business 3 days of receipt of completed baseline assessment forms. The administrative study coordinator will then notify the Tele-Savvy facilitator at each study site of the randomization result, and the facilitator will notify caregivers about the treatment group to which they are assigned. The statistician will provide the randomization scheme (random sorting using 10% maximum allowable deviation using PASS 2020 software⁵⁶), which will be applied after the baseline assessment. For the Tele-Savvy intervention, because 10 caregivers at each site must be assembled in order to convene a cohort, a window of up to 3 weeks will be allowed between randomization of a caregiver to that treatment group and initiation of the intervention. For the attention control group, caregivers will be permitted to access the Caregiving During Crisis program anytime beginning 3 days after randomization.

6.2.3 Follow-up Visits

Follow-up assessments will be sent electronically to caregivers for self-completion within the windows specified in the Table in Section 6.1. Identical assessments as completed at baseline (except Demographics) will be completed at the follow-up assessment points.

6.2.4 Completion/Final Evaluation

Potential reasons for early termination include unexpected serious illness or death of caregiver, voluntary withdrawal from the study by the caregiver, long-term nursing home admission of the older adults with ADRD, and death of the older adult with ADRD. Caregivers who terminate due to reasons other than death will be asked to complete follow-up assessments as appropriate to the time at which they terminate within their 6 months in the study. This follow-up assessment request will be sent electronically by the administrative study coordinator.

7 SAFETY ASSESSMENTS

7.1 Specification of Safety Parameters

Risks to study participants are primarily psychological in nature. They might experience distress while completing self-administered questionnaires, which ask about their experiences as caregivers and their emotional health and well-being. During the Tele-Savvy online classes, it is possible that caregivers will experience sadness, anxiety, anger, and other emotions during the process of sharing the ADRD journey that their spouses, parents, or other relatives/care recipients have traveled, as well as their own caregiving responsibilities. They also might become fatigued during the online classes as well as during the times between classes when they are viewing educational videos or doing their homework.

Protection against risks from self-administered questionnaires: Caregivers will be instructed to contact the Tele-Savvy facilitator and/or the study site clinician (Co-investigator [name] at UConn Health and Co-investigator [name] at Emory Healthcare), if they have concerns about questionnaire items causing distress or other psychological reactions. The facilitator and/or study site clinician will send administrative study coordinator the follow-up outcome status of these contacts for recording for study regulatory and reporting purposes.

Risks from participating in the Tele-Savvy program: The principal risk to participation is that the content and process may be emotionally-charged for participants and dealing with these materials may cause transient discomfort. However, it is remotely possible that such discomfort might persist and be observed by the facilitators to be serious in nature. Both facilitators are Licensed Clinical Social Workers with extensive experience working with distressed caregivers and are capable of assessing the seriousness of participants' discomfort. In such cases, facilitators will be instructed to note their observation to a participant and offer to refer him or her to the services of the clinicians on the study team if caregivers wish to speak with a clinician (Co-investigator [name] at UConn Health and Co-investigator [name] at Emory Healthcare). More generally, throughout the 7-week program, facilitators will introduce community-based resources and supports should caregivers feel distressed.

7.2 Methods and Timing for Assessing, Recording, and Analyzing Safety Parameters

All instances of psychological distress necessitating contact of clinicians on the study team will be recorded on case report forms by the study coordinator and will follow DSMB or Safety Officer and Institutional Review Board (IRB) of record guidelines for reporting.

7.3 Adverse Events and Serious Adverse Events

AE Definition: AE is any untoward or unfavorable medical occurrence in a human study participant, including any abnormal sign (e.g. abnormal physical exam or laboratory finding), symptom, or disease, temporally associated with the participants' involvement in the research, whether or not considered related to participation in the research.

AEs for this study include: As noted above, the only expected AEs with possibly deleterious outcomes for this study are risks of transient emotional upset experienced during completion of study questionnaires and/or in processing their caregiving situation during the course of participating in the group-based online course.

SAE Definition: SAEs consist of any adverse event that results in death; is life threatening or places the participant at immediate risk of death from the event as it occurred; requires or prolongs hospitalization; causes persistent or significant disability or incapacity; results in congenital anomalies or birth defects; is another condition which investigators judge to represent significant hazard

SAEs for this pilot study include:

No serious adverse events are expected. This is a very low risk study, principally involving participants being asked to complete an online program designed to enhance their caregiving self-efficacy and mastery when completing complex care tasks, and complete self-administered questionnaires.

7.3.1 Reporting Procedures

The Principal Investigator (PI) will be responsible for ensuring participants' safety on a daily basis. In addition, the NIA-appointed Safety Officer will oversee all data and safety monitoring activities for this study. The Safety Officer will act in an advisory capacity to the NIA Director to monitor participant safety, to evaluate the progress of the study, and to review procedures for maintaining the confidentiality of data, the quality of data collection, management, and analyses. Advarra IRB will conduct the ethical review required for the protection of human subjects.

Severity of Event

Mild: Awareness of signs or symptoms, but easily tolerated and are of minor irritant type causing no loss of time from normal activities. Symptoms do not require therapy or a medical evaluation; signs and symptoms are transient.

Moderate: Events introduce a low level of inconvenience or concern to the participant and may interfere with daily activities, but are usually improved by simple therapeutic measures; moderate experiences may cause some interference with functioning

Severe: Events interrupt the participant's normal daily activities and generally require systemic drug therapy or other treatment; they are usually incapacitating

Expectedness

- **Unexpected** - nature or severity of the event is not consistent with information about the condition under study or intervention in the protocol, consent form, product brochure, or investigator brochure.
- **Expected** - event is known to be associated with the intervention or condition under study.

Unexpected events will be subject to expedited reporting requirements as described in the [NIA Guidance on Clinical Trials](#) and in Section 1.2.3, below.

Relatedness

- **Definitely Related:** The adverse event is clearly related to the investigational agent/procedure – i.e. an event that follows a reasonable temporal sequence from administration of the study intervention, follows a known or expected response pattern to

the suspected intervention, that is confirmed by improvement on stopping and reappearance of the event on repeated exposure and that could not be reasonably explained by the known characteristics of the subject's clinical state.

- **Possibly Related:** An adverse event that follows a reasonable temporal sequence from administration of the study intervention follows a known or expected response pattern to the suspected intervention, but that could readily have been produced by a number of other factors.
- **Not Related:** The adverse event is clearly not related to the investigational agent/procedure - i.e. another cause of the event is most plausible; and/or a clinically plausible temporal sequence is inconsistent with the onset of the event and the study intervention and/or a causal relationship is considered biologically implausible.

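### The relatedness scale in 7.3.1 has no category for an adverse event that is new in nature, because both related categories require a response pattern that is already recognised

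*Combined protocol and SAP*

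**What the plan says.** Section 7.3.1 (Reporting Procedures) grades each event on severity, expectedness and relatedness, as three separate attributes. Relatedness has three levels.

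- **Definitely Related**: the event "follows a reasonable temporal sequence from administration of the study intervention, follows a known or expected response pattern to" the intervention, and it must be one "that is confirmed by improvement on stopping and reappearance of the event on repeated exposure". The caregiver's clinical state must also not reasonably explain it.
- **Possibly Related**: the event "follows a known or expected response pattern to the suspected intervention, but that could readily have been produced by a number of other factors". Its timing must be reasonable as well.
- **Not Related**: this level asks for a positive ground against causation. One ground is that something else is the likeliest cause; the others are inconsistent timing and the case where "a causal relationship is considered biologically implausible".

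There is no probable, unlikely or unassessable level.

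On what is already recognised, section 7.3 states that "the only expected AEs with possibly deleterious outcomes for this study are risks of transient emotional upset". Section 7.1 is wider. It names sadness, anxiety, anger, other emotions and fatigue, and adds that "it is remotely possible that such discomfort might persist and be observed by the facilitators to be serious in nature".

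**The concern.** A causality scale should be able to label any event, including one that nobody foresaw. Here both related levels ask whether the response is already recognised, which is close to the question that the expectedness item asks. Section 7.3.2 explains unexpected serious events as those not previously reported for the intervention. Such an event will often have no recognised pattern, so a related label is hardest to reach for the kind of event where the causality judgement matters most.

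The top level raises a second, smaller difficulty. A caregiver who leaves the program because of distress and does not return cannot show reappearance, however clear the link.

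At stake is the quality of the causality label in the adverse event material that goes to the Safety Officer (7.4) and to the quality control committee, which is asked to look for patterns of adverse events (10.3.2).

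**Working it through.** The point contains no figure to recompute. The check takes each definition as a list of conditions and asks which categories a given event can enter.

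**Conditions, from 7.3.1**

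| Category | Plausible timing | Recognised pattern | Other conditions |
|---|---|---|---|
| Definitely Related | required | required | better on stopping, returns on re-exposure, not explained by clinical state |
| Possibly Related | required | required | other factors could readily be the cause |
| Not Related | – | – | clearly unrelated: another cause most plausible, or timing inconsistent, or causation implausible |

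The pattern condition appears in 2 of the 2 related categories. Lack of a recognised pattern is not among the grounds for Not Related.

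**Test events**

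1. *Transient upset during a session.* This is the expected event in 7.3, so the pattern condition is met and Possibly Related is open.
2. *Distress more severe or more persistent than usual.* Section 7.3.1 defines unexpected by nature or by severity, so this event may count as unexpected. Section 7.1 nevertheless describes discomfort that persists and is serious, so it can be read as following a known pattern. Possibly Related is open. Panic could be read the same way, as a strong form of the anxiety that 7.1 names.
3. *Distress that makes a caregiver leave for good.* Definitely Related is closed, since reappearance cannot be shown. Possibly Related is open if the event fits a known pattern and other factors could readily have caused it. The second condition will usually hold, because 6.2.1 describes these stressors as common in caregivers' ordinary lives.
4. *An event new in nature, with plausible timing and no better explanation.* Definitely Related fails on the pattern condition. Possibly Related fails on the same condition. Not Related fails because none of its grounds is met. The event fits 0 of 3 categories.

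Only the fourth type is uncodable.

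**What depends on the label**

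- Capture: the definition in 7.3 counts an event whether or not it is thought related, and 7.2 records all distress that leads to contact with a study clinician.
- Reporting (7.3.2): unexpected serious events go by the expedited route, deaths within 24 hours, other serious events quarterly, and adverse events at least every 6 months. None of these routes states a relatedness condition.
- Review: all events are discussed at weekly team meetings (7.3.2).
- Analysis: section 9.5 plans no tabulation or test of harms by relatedness.

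**Check of the repair**

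Suppose Possibly Related required only reasonable timing and that the intervention or a study procedure could have contributed. An event outside Not Related has consistent timing, a causal link that is not implausible and no other cause that is most plausible. It then meets the revised definition, so every event has a category, including the fourth test event.

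**The case against.** The strongest reply is that the gap is narrow and that little hangs on it. The pattern condition is met by a known or an expected response, so it is wider than the short list in 7.3. The account in 7.1 covers most reactions that a psychoeducational program is likely to provoke. All events are still captured and reported. A strict top category is a legitimate choice, and a caregiver who stops because of distress can normally be placed in the middle one. Section 7.3.2 also ties reporting to NIA guidelines that are not reproduced, so it is not clear how freely the sponsor may reword the scale. All of this stands, and it limits the consequence. It does not supply a category for an event that is new in nature.

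Three stronger readings are tempting, and the documents do not support them.

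- A reader might infer that no unexpected event can be coded as related. Unexpected includes unexpected severity, and an event of that kind can follow a known pattern.
- A reader might infer that the scale pushes events into Not Related. That category is for events where "The adverse event is clearly not related to the investigational agent/procedure", and no text makes it the default. A lean would arise only if the form forces a choice and raters settle there, and the documents establish neither.
- A reader might infer that a planned harms summary, or the low-risk case for offering Tele-Savvy routinely, is biased by the definitions. No summary by relatedness is planned, and low risk is an advance description of the program rather than a conclusion to be drawn from this coding.

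**Conclusion.** The concern holds in a limited form. As written, the three categories are not exhaustive and are not independent of expectedness. An event that is new in nature, plausibly timed and without a better explanation cannot be coded at all. The mandatory re-exposure condition also closes Definitely Related to caregivers who leave and do not return, but that is a secondary matter because Possibly Related normally remains available to them.

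The size is a missing or unreliable causality label for such events. No report is lost under the stated schedule and no planned estimate changes. How many events would be affected cannot be derived from the documents, and none may occur in a trial with 60 Tele-Savvy caregivers.

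The conclusion rests on a literal reading of the definitions and on counting the distress described in 7.1 as a known pattern. If only the transient upset of 7.3 counted, the gap would be wider. The statement that relatedness filters nothing covers the protocol's own text; the IRB policies and NIA guidelines that it cites could not be examined. The change is worth making because the defect is plain and the repair costs almost nothing.

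**What to change.** In 7.3.1 and on the adverse event form, define Possibly Related as an event with a reasonable time sequence to which the intervention or a study procedure could have contributed, whether or not the pattern of response is already known. Leave Not Related as it stands. Expectedness then remains a separate item, and every event has a category.

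Optionally, treat improvement on stopping and reappearance on re-exposure as supporting rather than mandatory evidence for Definitely Related.

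Before adopting the wording, the sponsor should confirm that it agrees with the NIA guidelines cited in 7.3.2. The cost is one or two sentences in 7.3.1 and on the form, with the facilitator and coordinator training brought into line. A few more events will be coded Possibly Related. Sample size, visits and analyses do not change.

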7.3.2 Follow-up for Adverse Events

The study will adhere to the reporting requirements for AEs and SAEs stipulated in the [NIA Adverse Event and Serious Adverse Event Guidelines](#) as outlined below.

Process for identifying AEs and SAEs:

Facilitators of the Tele-Savvy programs in Connecticut and Georgia will receive training in AEs and SAEs and reporting procedures as part of their Tele-Savvy training. Within 24 hours of learning about any AEs or SAEs, facilitators will contact the study coordinator at UConn Health ([name]), who will complete a study form for collection of AE and SAE information. The study coordinator will report SAEs within 24 hours of learning about them to the PI ([name]), will submit unexpected SAEs within 24 hours of learning about these events to the parties specified in the following section of this DSMP, and will submit all other SAEs to the parties noted in the following section on a quarterly basis, unless otherwise requested by the the NIA-appointed Safety Officer. All AEs and SAEs will be discussed during weekly study team meetings that will include key personnel from both sites and the study coordinator.

Adverse event reporting schedule:

Although no SAEs are expected due to the very low risk of the Tele-Savvy interventions, we will adhere to the following reporting schedule:

- All **adverse events that are both serious (SAE) and unexpected** (i.e., have not been previously reported for the study's intervention) will be reported to the IMPACT Collaboratory Regulatory and Data Team Leader ([name]), Advarra IRB, NIA IMPACT Collaboratory PO ([name]), and the NIA-appointed Safety Officer of the study's knowledge of SAE.
- The summary of all other SAEs will be reported to IMPACT Collaboratory Regulatory and Data Team Leader ([name]), Advarra IRB, NIA IMPACT Collaboratory PO ([name]), and the Safety Officer quarterly, unless otherwise requested by the Safety Officer.

- All deaths will be reported to IMPACT Collaboratory Regulatory and Data Team Leader ([name]), Advarra IRB, NIA IMPACT Collaboratory PO ([name]), and the Safety Officer within 24 hours of study's knowledge of death.
- AEs will be reported per IRB policies and also to IMPACT Collaboratory Regulatory and Data Team Leader ([name]), Advarra IRB, NIA IMPACT Collaboratory PO ([name]), and the Safety Officer at minimum every 6 months, or at a frequency requested by NIA and/or Safety Officer.

7.4 Safety Monitoring

The Principal Investigator (PI) will be responsible for ensuring participants' safety on a daily basis. In addition, the NIA-appointed Safety Officer will oversee all data and safety monitoring activities for this study. The Safety Officer will act in an advisory capacity to the NIA Director to monitor participant safety, to evaluate the progress of the study, and to review procedures for maintaining the confidentiality of data, the quality of data collection, management, and analyses. Advarra IRB will conduct the ethical review required for the protection of human subjects.

8 INTERVENTION DISCONTINUATION

We do not anticipate discontinuing this study because the intervention has been tested in an efficacy trial that was successfully completed.

Caregivers may withdraw voluntarily from participation in the study at any time and for any reason. We will continue to follow them, with their permission, even if the study intervention is discontinued. If modifications are required to the planned follow-up schedule due to temporary or permanent discontinuation of caregivers from the intervention, we will document accordingly and make every effort to complete one or both follow-up assessment points.

Replacement of subjects who discontinue will not be done in this study.

9 STATISTICAL CONSIDERATIONS

9.1 General Design Issues

Statistical hypothesis: Caregivers who participate in the Tele-Savvy intervention will experience greater improvement in *caregiver mastery* between baseline and 3 month follow-up compared to caregivers who receive the self-guided, online Caregiving During Crisis program.

Secondary hypotheses: Caregivers who participate in the Tele-Savvy intervention will experience greater improvement in *reactions to behavioral and psychological symptoms of ADRD and in caregiver stress* between baseline and 3 month follow-up compared to caregivers who receive the self-guided, online Caregiving During Crisis program.

In this pilot pragmatic clinical trial, our primary goal is to successfully enroll caregivers invited to participate in this study by clinical sites in health care systems within the daily workflow of clinical activities. Within the one-year time frame allowed for this pilot study, we determined that we could enroll, at each of the two clinical sites, 3 sequential Tele-Savvy programs. We further determined that we could introduce an attention control condition and randomly assign caregivers to receive Tele-Savvy or the control condition in waves, each wave representing a

caregivers participating in a distinct Tele-Savvy program and a comparison group of caregivers receiving the Caregiving During Crisis program.

